#### 2.4 Efficacy, Safety, and Other Variables

#### 2.4.1 Co-Primary Endpoints

- There are two primary efficacy endpoints:
  - Within-participant change in ADAS-Cog 11 from baseline to week 48 of the doubleblind phase, compared between the treatment group and the placebo group
  - Within-participant change in CDR-Sum of Boxes from baseline to week 48 of the double-blind phase, compared between the treatment group and the placebo group

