## **4 STATISTICAL METHODS**

#### 4.1 Sample Size Justification and Power

#### 4.2 Overall Study Power

Using approximately 336 randomized participants (with a 1:1 assignment approximately 168 per arm), this study has at least 80% power to reject the null hypothesis of no efficacy in favor of the alternative that BHV4157 is efficacious, given the assumption of a difference in the mean change from baseline to 12 months between the BHV-4157 arm and placebo arm of 2.64 points on the ADAS-Cog 11 and 0.95 points in CDR-SOB, and under a range of interim effect sizes which give 93.7% probability of proceeding at the interim analysis.

This calculation assumes no more than a 26% dropout rate, which would leave  $336 \times 0.74 = 248$  subjects available at the final analysis, or 124 per arm. The calculation also assumes a standard deviation of 6 points on the change in ADAS-Cog 11 in each arm at both 6 months and 12 months, and a standard deviation of 2.3 points on the change in in CDR-SOB at 12 months; in addition a correlation of 45% between 12-month-change on the co-primary ADAS-Cog11 and CDR-SOB endpoints is assumed. These assumptions are supported by published retrospective data from historical ADCS studies. The computations use a 2-sided 2-sample t-test at 5% alpha to approximate power.

Briefly, the statistical reasoning is as follows:

- 1. P(pass overall) = P(pass final | pass interim) P(pass interim) ≥ P(pass final) P(pass interim)
- 2. P(pass final) = P(pass final ADAS) P(pass final CDR | pass final ADAS)
- 3. Numerical integration shows that P(pass final CDR | pass ADAS) is about 3% greater than P(pass final CDR), given the assumed 45% correlation between these endpoints.

Hence, if P(pass interim) = 0.937, P(pass final ADAS) = 0.92, and P(pass final CDR) = 0.90, then P(pass overall)  $\ge 0.92 \text{ x} (1.03 \text{ x} 0.90) \text{ x} 0.937 = 0.80.$ 

With 124 subjects per arm, the unconditional power for the ADAS-COG endpoint is 92%, if the mean difference in change is 2.64 points with standard deviation of 6 points within each arm. At this sample size, the unconditional power for the CDR-SOB endpoint is 90%, if the mean difference is 0.95 points with standard deviation of 2.3 points within each arm. Hence, if the interim analysis has power 0.937 or greater to pass, the overall power is 80% or more following the statistical reasoning given above.

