#### 4.3.1.2 Data Handling

All output will be incorporated into Microsoft Excel or Word files, sorted and labeled according to the International Conference on Harmonization (ICH) recommendations, and formatted to the appropriate page size(s).

Tabulations will be produced by randomized treatment group and overall, unless otherwise specified.

Categorical variables will be tabulated with counts and percentages. Continuous variables will be summarized with univariate statistics (e.g., n, mean, standard deviation (SD), median, minimum, and maximum). The minimum and maximum will be presented with the same precision as the data, the mean and percentiles will be presented with the precision of the data + 1 decimal place, and the SD will be presented with the precision of the data + 2 decimal places.

Unless otherwise specified, all statistical tests will be 2-sided with alpha = 0.05. Tests will be declared statistically significant if the calculated p-value is  $\leq 0.05$ . P-values < 0.0001 will be presented as "<0.0001". Otherwise, p-values will be presented to 4 decimal places.

Change from baseline is calculated by subtracting the baseline value from the observed postbaseline value at any subsequent visit. Baseline (specific to the randomized phase or to the open-label phase) will be defined as last available assessment on or before the 1st day the participant receives study medication for that phase. Tabulations of the following endpoints will present the number of unique participants with an event: protocol deviations; non-study medications; AEs; and laboratory abnormalities. Thus, for these endpoints, multiple occurrences of the same event are counted only once per participant.

Unique Participant ID's will take the form "BHV4157-203-site#-participant#". By-participant listings will display unique PID and "(Age/Sex/Race)" stacked together in the same column using the following conventions:

- Age at informed consent will be displayed truncated to an integer
- Sex will be displayed abbreviated as "F" for female and "M" for male
- Race will be abbreviated as "A" for Asian", "B" for Black or African American, "I" for American Indian or Alaska Native, "M" for multiple, "N" for Native Hawaiian or Other Pacific Islander, and "W" for White

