# APPENDIX 2 - Calculating the ADAS-Cog Total Score when there are missing data

The ADAS-Cog is a rater-administered scale with eight performance subtests: Word Recall; Commands; Constructional Praxis; Naming; Ideational Praxis; Orientation; Word Recognition; Remembering Word Recognition Test Instructions. Three examiner ratings, of Spoken Language, Language Comprehension, and Word Finding Difficulty, also are obtained. The test is scored in terms of errors, with higher scores reflecting poorer performance and greater impairment. Scores can range from 0 (best) to 70 (worst).

If a participant is unable to complete any of the eight performance subtests, the rater must code the reason for incompletion:

- Not done for reasons other than physical or cognitive
- Participant refused
- - Participant unable to complete for physical reasons
- - Participant unable to complete for cognitive reasons

When total scores for performance subtest measures are missing because the participant is unable to complete the task for cognitive reasons, the worst possible score for the measure will be assigned.

Because Remembering Test Instructions is scored solely based on performance on Word Recognition, if Word Recognition was not completed for any reason, then Remembering Test Instructions must also be scored as not completed.

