#### For the ADAS-Cog Total Score

The total score is the sum of 11 subscales (8 performance subtests and 3 examiner ratings). If more than two subscales (either performance subtest or examiner ratings) are missing or more than 2 performance subtests have partial missing data or if both the Word Recall and Word Recognition subtests are missing, then the ADAS-Cog total score will be missing. Otherwise, the total score will be based on the sum of the scores from the non-missing subscales multiplied (prorated) by the ratio (max ADAS-cog Total Score of 70/max total possible from non-missing subscales).

ADCS & Biohaven Pharmaceuticals Protocol BHV4157-203

For example, if the Word Recall performance subtest , which ranges from 0-10 (maximum=10), is missing, and another subtest Commands, which ranges from a score of 0-5 (maximum = 5) is also missing, then the total ADAS-cog score will be calculated as the sum from the 9 non-missing subscales multiplied by the ratio (70/(70 - (10 + 5)) = 70/55 = 1.27), the resulting prorated total score will be rounded up to the nearest integer

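### SAP Appendix 2 rounds prorated ADAS-Cog 11 totals upward: a small, needless error on a co-primary score, in wording that can be coded two ways

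*SAP*

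**What the plan says.** ADAS-Cog 11 is one of two co-primary endpoints: "Within-participant change in ADAS-Cog 11 from baseline to week 48" (SAP 2.4.1). On direction, SAP Appendix 2 states: "The test is scored in terms of errors, with higher scores reflecting poorer performance and greater impairment". Change is formed as post-baseline minus baseline (SAP 4.3.1.2): "Change from baseline is calculated by subtracting the baseline value from the observed postbaseline value at any subsequent visit".

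Appendix 2 sets the total to missing under these conditions: "If more than two subscales (either performance subtest or examiner ratings) are missing or more than 2 performance subtests have partial missing data", or when Word Recall and Word Recognition are both absent. Otherwise the sum of the available subscales is "multiplied (prorated) by the ratio (max ADAS-cog Total Score of 70/max total possible from non-missing subscales"). The worked example has Word Recall (maximum 10) and Commands (maximum 5) missing and gives the factor "70/(70 - (10 + 5)) = 70/55 = 1.27". At the end of that example comes the rounding instruction: "the resulting prorated total score will be rounded up to the nearest integer". It does not appear in the general rule. No other section gives a different rule or a reason for rounding upward.

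The same appendix gives the worst possible score to a performance subtest that could not be completed for cognitive reasons. Such a subtest is therefore not treated as missing.

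**The concern.** A ceiling can only raise a score or leave it alone, and on this scale higher is worse. Within the appendix the step applies to prorated totals and not to complete ones, so the two kinds of record are scored on slightly different footings. The analysis model (SAP 4.8.3) treats change as a continuous outcome and does not need integers. The proration rules for ADCS-ADL (SAP 4.8.4.2) and for the neuropsychological composite (SAP Appendix 3) mention no rounding.

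ADAS-Cog 11 is also tested first in the gatekeeping sequence, so its scoring should be unambiguous. Here it is not: the phrase joins the language of a ceiling to the language of ordinary rounding, and two programmers could follow it and produce different totals from the same data.

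**Working it through.** **Inputs.** Scale maximum 70, the proration formula and the example ratio are from SAP Appendix 2. Difference 2.64, SD 6, 124 per arm and stated power 92% are from SAP 4.2, which also gives the test: "The computations use a 2-sided 2-sample t-test at 5% alpha to approximate power". The proration rate is in neither document and is assumed below.

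**Plan's own figures.**
- Ratio: 70/55 = 1.2727, stated as 1.27. Reproduced.
- SE of the contrast: 6 × √(2/124) = 0.762. ADAS-Cog power: Φ(2.64/0.762 − 1.96) = 93.4% (noncentral t: 93.2%), against 92% stated. Close enough to count as reproduced.

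**Error per prorated total.** For each integer raw sum s from 0 to the available maximum M, the error is ceil(70s/M) − 70s/M.

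| Points missing | M | Raw sums | Mean error | Largest error | Sums where ceiling and nearest differ |
|---|---|---|---|---|---|
| 5 | 65 | 66 | 0.455 | 0.92 | 30 |
| 10 | 60 | 61 | 0.410 | 0.83 | 20 |
| 15 | 55 | 56 | 0.446 | 0.91 | 25 |

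The error is never negative. Leaving out the five lowest and five highest sums gives means of 0.464, 0.412 and 0.457, hence the range 0.41 to 0.46. Each raw sum is weighted equally, because the documents give no score distribution.

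Examples at M = 55: a sum of 20 gives 25.45, scored 26 by ceiling and 25 by nearest; 26 gives 33.09, scored 34 or 33; 22 gives exactly 28 under both.

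**Effect on the change score.** If only Week 48 is prorated, change is too high by the error. If only baseline is prorated, change is too low by it. If both are prorated, the two errors tend to offset.

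**Effect on the arm contrast.** For Week 48 totals, shift = mean error × (active rate − placebo rate).
- Equal rates: 0.
- 10% versus 5% (assumed): 0.05 × 0.45 = 0.0225, about 0.02 points.
- 20% versus 10%, or 10% versus 0% (assumed): 0.10 × 0.45 = 0.045; with the mean error taken as 0.5, 0.05 points.

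Relative to the plan, 0.02 is under 1% of 2.64 and about 3% of the SE. A shift of 0.05 against the drug would lower the power from 93.4% to 92.5%.

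**Alternatives.** Without rounding the error is zero. Rounding to nearest gives mean error 0 at M = 65 and M = 55, with no error above 0.46. At M = 60, exact halves occur; if they go up, the mean is +0.08 and the largest error 0.5.

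**The case against.** Four things can be said for leaving the rule alone, and most of them stand.

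- *It is immaterial.* The rule is prespecified, applies identically to both arms, and moves the contrast by hundredths of a point even under assumed imbalances. This stands, and it caps the importance of the point.
- *It is probably loose wording for ordinary rounding.* Possibly so. The systematic shift would then nearly vanish, but the sentence would still need correcting.
- *Whole-number totals are a familiar scoring convention.* That is a fair reason to round, but not a reason to round only upward.
- *The most worrying route to imbalance is largely closed.* A reader might infer that patients who decline more will have more prorated totals, so that the error would follow the treatment effect. The documents do not support this. Performance subtests not completed for cognitive reasons take the worst score and are not themselves prorated. What remains is mainly refusal, physical inability, other non-cognitive reasons, subtests with more than 25% of items missing, and missing examiner ratings. Nothing guarantees that these are balanced between arms, but nothing suggests that they are not.

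A reader might also infer that the endpoint is pushed in one direction. It is not: the error has a fixed sign on a single score, but in the change score its sign depends on which visit was prorated.

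**Conclusion.** The point holds as a minor one. As written, the rule is a ceiling that adds 0.41 to 0.46 points on average, and at most about 0.92, to a prorated total with 5, 10 or 15 points missing. It biases the arm contrast only if proration at a given visit is more frequent in one arm, and then by about 0.02 to 0.05 points under the assumed rates. If the active arm has more prorated Week 48 totals the shift goes against the drug; if the placebo arm has more, it goes in the drug's favour. The documents do not show which, if either, applies.

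It would be wrong to conclude that the rule threatens the planned power or tilts the trial toward one arm. The sizes rest on the literal reading, equal weight on integer raw sums, and proration rates that are assumptions. Item-level proration within a subtest can also give fractional sums, which the enumeration does not cover. The case for change is that the step serves no need of the model and leaves the scoring of a co-primary endpoint open to two readings.

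**What to change.** Delete the rounding clause from the worked example in SAP Appendix 2, and state in the general rule for the ADAS-Cog total that the prorated total is analysed unrounded. If integer totals are preferred, specify rounding to the nearest integer in the general rule, say how exact halves are treated, and say whether the rule also covers totals made fractional by item-level proration.

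The cost is a one-clause edit and the matching line of scoring code, made before unblinding. It needs no new data and leaves the model and the sample size as they are.

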# APPENDIX 3 - Calculating the composite neuropsychological test battery score when there are missing data

A cognitive composite outcome measure will be computed using measures from the NACC Neuropsychological Test Battery. The composite outcome will comprise the overall average of the Z-scores from each of the following NACC subtest measures: Craft Story 21 total immediate Recall; Craft Story 21 total delayed recall; Benson Figure copy score; Benson Figure delayed recall; Multilingual Naming Test total correct; Letter Fluency total score; Category Fluency total score; Trail Making Test A time to completion; Trail Making Test B time to completion; Number Span Forward total correct; and Number Span Backward total correct. Z-scores for each participant on each measure will be calculated using the overall average of all participants at baseline as reference.

Missing total scores for subtest measures from the NACC Neuropsychological Test Battery are designated as missing for the following reasons:

- Participant Unable for Cognitive Reasons
- • Participant Unable for Other Reasons (Physical, auditory, etc.)
- · Participant/Study Partner Refused
- · Oversight
- · Other Reason
- · Unknown

When total scores for subtest measures are missing because the participant was unable to complete the task for cognitive reasons, the worst possible score for the measure will be assigned. Total scores that are missing for any other reason will be treated as missing in calculating the composite neuropsychological test battery score.

For partially missing (item-level) missing data, if fewer than 25% of items within a NACC subtest measure are missing, scores for the missing items will be prorated as the average of the completed items on that subtest. This procedure will be employed for a maximum of two NACC subtests. If more than 25% of the items within any NACC subtest are missing, the entire subtest is missing.

The total composite neuropsychological test battery score will be calculated as the overall average Z-score from each of the completed subtests. If more than 2 NACC subtests are missing, the total composite neuropsychological test battery score will be missing.
